## 10.4 Efficacy Subgroup Analyses

The following efficacy variables will be analyzed as described in Section 10.2 by pooling subjects with active and inactive uveitis at start of Study M11-327

- Proportion of subjects with no active lesions in both eyes at each study time point.
- AC cell grade (mean of both eyes) at each study time point.
- Proportion of subjects with a Grade  $\leq 0.5+$  in AC cells in both eyes on Slit Lamp Exam, according to SUN criteria at each study time point.
- VH grades (mean of both eyes) at each study time point.
- Proportion of subjects at each study time point with Grade  $\leq 0.5+$  in vitreous haze in both eyes on indirect ophthalmoscopy, according to NEI/SUN criteria.
- Proportion of subjects at each study time point in quiescence defined as no active lesions, AC  $\leq 0.5$  and VH  $\leq 0.5$ .
- LogMAR Best corrected visual acuity (BCVA) (mean of both eyes) at each study time point.
- Proportion of subjects who started IMMs in Study M11-327.
- Systemic CS dose at each study time point.
- Proportion of subjects with steroid-free quiescence at each study time point.
- OCT evidence of macular edema in at least one eye at each study time point.
- Central retinal thickness (mean of both eyes) at each study time point by OCT machine.

in the following subgroups:

- Gender (male/female)

- Duration of uveitis (< 1,  $\geq$  1 years)
- Type of uveitis (intermediate versus posterior versus panuveitis)
- Diagnosis (idiopathic/other versus birdshot choroidopathy versus multifocal choroiditis and panuveitis versus Vogt Koyanagi Harada versus sarcoid versus Behcet's)
- IMM usage at Baseline of Study M11-327 (yes, no)

In addition, the efficacy variable "Proportion of subjects at each study time point without a worsening of BCVA by  $\geq$  15 letters on the ETDRS in both eyes relative to Baseline for subjects who had inactive uveitis when they entered the study and to Week 8 for subjects who had active uveitis when they entered the study" will be analyzed as described in Section 10.2 in the following subgroups:

- Subjects with/without AE "posterior capsule opacification/rupture"

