5.0 Investigational Plan

5.1 Overall Study Design and Plan: Description

This study is a Phase 3, open-label multicenter study designed to evaluate long-term safety and efficacy of adalimumab in adult subjects with non-infectious intermediate-, posterior-, or pan-uveitis who have either discontinued from Study M10-877 or Study M10-880 for having met "Treatment Failure" criteria or have successfully completed Study M10-877 or Study M10-880. Subjects who prematurely discontinue from Study M10-877 or Study M10-880 for reasons other than for Treatment Failure as defined in the parent protocol, will not be eligible for this study.

Figure 1. Study Schematic

* Visits will occur every 12 weeks following Week 66 until the end of the study (not to exceed 15 March 2018).

Subjects rolling over from Study M10-877 and Study M10-880 will be evaluated for entry into this study at the final or last visit in the parent study. Therefore, Study M11-327 Baseline (Week 0) visit will be performed on the same day as the Final/Early Termination visit in the parent studies. At this visit, after administering and obtaining the subject's consent, subjects will be evaluated to ensure they meet all inclusion criteria and none of the exclusion criteria listed in Section 5.2. If the Baseline visit occurs greater than (>) 14 days after the Final/Early Termination visit of the parent study, all procedures listed in the Baseline visit must be completed. The maximum amount of time allowed between the Final/Early Termination visit of the parent study and the Baseline visit of Study M11-327 is 28 days.

Starting at Baseline, all subjects will receive open-label adalimumab 40 mg dose eow SC regardless of treatment assignment in the randomized, double-masked Study M10-877 or Study M10-880.

As subjects who discontinue from Study M10-877 or Study M10-880 due to "Treatment Failure" will have active disease on study entry into Study M11-327, concomitant therapy with corticosteroids (oral or topical) and/or any one of the immunosuppressive therapies permitted in Study M10-877 and Study M10-880, will be allowed as necessary to control intraocular inflammation.

Subjects who successfully complete Study M10-877 or Study M10-880 and have inactive disease at time of entry into Study M11-327 may continue, taper and/or discontinue concomitant corticosteroids and/or immunosuppressive therapy which were permitted in Study M10-877 and Study M10-880 based on the investigator's clinical judgment.

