## **7.0                    Demographics, Baseline Characteristics, Medical History, and Previous/Concomitant Medications**

The subsequently described analyses will be provided by active uveitis (defined as having discontinued the parent study, Study M10-877/M10-880 due to Treatment Failure) versus inactive uveitis and overall in the ITT set.

All statistical analyses will be descriptive. Descriptive statistics will include the number of observations, mean, standard deviation, minimum, first quartile, median, third quartile, and maximum for continuous variables; and counts and percentages for discrete variables.

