## **10.0 Efficacy Analysis**

### **10.1 General Considerations**

The subsequently described analyses will be provided in the ITT set. All statistical analyses will be descriptive. Results will be stratified between subjects who entered into the study with active versus inactive uveitis. For subjects who had inactive and subjects who had active uveitis when they entered the study, the efficacy analyses will start at Baseline of Study M11-327. Results will also be provided overall except for efficacy variables defined differently for subjects entering Study M11-327 with active and inactive uveitis.

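### Efficacy subgroups in SAP 10.4 are shown only pooled over active and inactive entrants, so differences between subgroup levels may partly reflect entry status

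*SAP*

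**What the plan says.** For the main efficacy results, SAP 10.1 states: "Results will be stratified between subjects who entered into the study with active versus inactive uveitis". It then adds pooled results beside the stratified ones: "Results will also be provided overall except for efficacy variables defined differently for subjects entering Study M11-327 with active and inactive" uveitis. For both groups, "the efficacy analyses will start at Baseline of Study M11-327".

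SAP 10.4 takes twelve of the SAP 10.2 variables and analyses them in five sets of subgroups: gender, duration, type, diagnosis and baseline IMM use. It does so "by pooling subjects with active and inactive uveitis at start of Study M11-327". It asks for no version by entry status, no standardisation and no count of active and inactive entrants within the subgroup levels. A separate paragraph on loss of visual acuity, split by one adverse event, does not carry the pooling wording and is outside this point.

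SAP 7.0 defines the split as "active uveitis (defined as having discontinued the parent study, Study M10-877/M10-880 due to Treatment Failure) versus inactive uveitis". Protocol 5.1 says that Treatment Failure subjects "will have active disease on study entry into Study M11-327". Among the pooled outcomes is the "Proportion of subjects at each study time point in quiescence defined as no active lesions" together with low anterior chamber cell and vitreous haze grades.

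**The concern.** The two entry groups start from opposite disease states. Several pooled outcomes (no active lesions, cell grade, haze grade, quiescence) measure the activity that separates them, and they are tabulated from Baseline on. A subgroup level that holds more active entrants will therefore tend to look worse at Baseline and probably at early visits, whatever the subgroup factor does.

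The difference need not fade. Under Protocol 5.1, active entrants whose flare is not controlled in the first 8 weeks may leave the study. Under SAP 6.3.1 every missing binary value then counts as non-response, so early departures can weigh on a subgroup at later visits. Protocol 5.1 also allows active entrants corticosteroids as needed, which touches steroid dose and steroid-free quiescence.

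At stake is interpretation. Side-by-side subgroup tables with 95% confidence intervals invite comparison, and a gap produced by a different mix of entrants could be read as a difference between diagnoses or as an association with IMM use.

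**Working it through.** The plan states no figure to reproduce. It gives no outcome rates by entry status and no active/inactive split by subgroup. The rates and shares below are assumptions that show the mechanism.

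**Formula.** Let a be the share of active entrants in a subgroup level, and let P(act) and P(inact) be the response rates by entry status, the same at both levels (no subgroup effect).

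- Pooled rate = a × P(act) + (1 − a) × P(inact)
- Spurious gap = (difference in a) × (P(inact) − P(act))

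**Main illustration**, with P(act) = 60% and P(inact) = 85%:

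| Active shares | Pooled rates | Gap (points) |
|---|---|---|
| 60% vs 60% | 0.60×60 + 0.40×85 = 70.0% at both levels | 0 |
| 40% vs 70% | 0.40×60 + 0.60×85 = 75.0%; 0.70×60 + 0.30×85 = 67.5% | 0.30 × 25 = 7.5 |
| 30% vs 80% | 0.30×60 + 0.70×85 = 77.5%; 0.80×60 + 0.20×85 = 65.0% | 0.50 × 25 = 12.5 |

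**Wider range**, gap in points:

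| Response, active / inactive | Shares 60 vs 60 | 65 vs 55 | 70 vs 50 | 80 vs 40 |
|---|---|---|---|---|
| 60 / 60 | 0 | 0 | 0 | 0 |
| 50 / 70 | 0 | 2 | 4 | 8 |
| 40 / 80 | 0 | 4 | 8 | 16 |
| 30 / 90 | 0 | 6 | 12 | 24 |
| 0 / 100 (limiting case at Baseline) | 0 | 10 | 20 | 40 |

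The gap vanishes if either the shares or the response rates are equal.

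**Scale against sampling error.** For the planned 400 subjects split 200 vs 200, with a response near 56%, the half-width of a 95% interval for a difference is 1.96 × √(0.56 × 0.44 × 2/200) = 9.7 points. For 100 vs 300 it is 11.2 points. A 7.5-point artefact lies within that noise; 12.5 points does not.

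**Where unequal shares are plausible.** Protocol 5.1 lets active entrants receive one permitted IMM as needed to control inflammation. SAP 7.5 counts a drug as concomitant at baseline if it started on or before the day of the first dose and had not stopped before it. An IMM begun on that day because of Treatment Failure therefore puts the subject in the IMM-yes group. Inactive entrants may also be continuing an IMM, so the documents fix neither the direction nor the size of the imbalance. For gender, duration, type and diagnosis they give no reason to expect one, and none to exclude it.

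**With the remedy.** Within each entry stratum the gap is 0 by construction. Standardised to a common mix, say 60% active, both levels give 0.60 × 60 + 0.40 × 85 = 70.0%, again a gap of 0.

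**The case against.** The pooling is deliberate and has a case. All efficacy analyses are descriptive, no test between subgroups is planned, the study has one arm, and its primary objective is safety. A pooled figure validly answers a descriptive question, such as what share of subjects with a given diagnosis was quiescent. The 10.4 list leaves out the variables defined against a different reference point by entry status, in line with SAP 10.1, and the stratified main results remain. Stratifying would also leave other imbalances, such as parent-study treatment.

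Pooling protects cell size as well. Retinal thickness is already split by OCT machine: three machines × three types × two entry states make 18 cells, about 22 subjects each (400/18) even before the ITT exclusions.

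Finally, the Section 7 baseline tables are planned by entry status, so a reader could work out much of the mix for gender, diagnosis, type and IMM use. They would not give it for the duration cut at 1 year, and type is grouped differently there.

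Most of this stands, and it keeps the point minor. It does not remove the point: leaving out variables with different reference points does nothing about a different mix, and knowing the mix does not show the response by entry status within a subgroup level.

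Three stronger readings are tempting and are not supported:

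- A reader might infer that entry status is the strongest known determinant of outcome. The documents rank no determinants; they only use entry status to stratify the main efficacy results.
- A reader might infer that the subgroup contrasts are confounded as a matter of fact. That needs unequal active shares, which the documents do not show.
- A reader might infer that sparse cells matter only for diagnosis. No counts are given, and Protocol 3.2 describes intermediate uveitis as the least common type in general, so type may be affected too.

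**Conclusion.** The point holds as a possibility that the planned subgroup tables give no means of assessing. SAP 10.4 drops the stratification that SAP 10.1 applies, for outcomes linked to entry status at Baseline. Pooled differences between subgroup levels may therefore partly reflect the mix of entrants, most plausibly for baseline IMM use.

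In the main illustration the size is 0 to 12.5 points. Over the wider post-entry assumptions it is 0 to 24 points, with up to 40 in the limiting case at Baseline. All of these rest on assumed rates and shares and on no true subgroup effect. The main efficacy results and the safety conclusions are not affected. This is a worthwhile improvement, not a necessary correction.

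**What to change.** Keep the pooled tables in SAP 10.4 and add:

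1. The number of active and inactive entrants within every level of every subgroup factor.
2. Results by entry status, beside the pooled ones, for gender, duration, type and baseline IMM use.
3. For diagnosis, and for any other level with few subjects in one entry stratum, the counts plus a proportion or mean directly standardised to the active/inactive mix of the whole ITT set. Give the standardised figure only where both strata hold enough subjects, with that minimum written into the SAP before the tables are run. Where a stratum is empty or too small, standardisation is undefined or unstable; show the pooled figure and label it as not adjusted for entry status.

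No new data are needed. The cost is more tables and wider intervals within strata. Even then the comparisons are balanced only for entry status, and the report should say so.

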## **11.0 Safety Analysis**

The subsequently described analyses will be provided overall in the safety set.

### **11.1 Treatment-Emergent Adverse Events**

Treatment-emergent adverse events (AEs) are defined as any event with an onset date that is on or after the first dose of adalimumab in Study M11-327 and no more than 70 days after the last dose of study drug administration.

If an incomplete onset date was collected for an AE, the event will be assumed to be treatment emergent unless there is other evidence that confirms that the event was not treatment emergent (e.g., the event end date was prior to the study drug start date). In case of increasing severity of an existing AE, the worsening will be considered as a new AE with a new onset date.

AE data will be summarized using primary MedDRA system organ classes (SOCs) and preferred terms (PTs) according to the most current implemented version of the MedDRA

coding dictionary. The SOCs will be presented in alphabetical order and the PTs will be presented in alphabetical order within each SOC. For AEs with an incidence rate  $\geq 5\%$  in the adalimumab group and SAEs, the PTs will also be presented in decreasing frequency.

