A repeat ANA/Anti-ds-DNA would be warranted if a subject has clinical signs and symptoms suggestive of lupus. The Anti-ds-DNA antibody testing will be performed in case of a positive ANA result.

All samples will be sent to the central laboratory for processing.

Adverse Events

Adverse events will be assessed at every study visit from Baseline through the Final/Early Termination visit, and during the 70-day phone call or clinic visit (if applicable). A phone

call or routine clinic visit should occur approximately 70 days after last dose of study medication to obtain follow-up information on any ongoing or new adverse events (Section 6.0 and Appendix D).

Any ongoing adverse events at the time of the Termination visit in the previous Study M10-877 or Study M10-880 will be automatically transferred onto the Study M11-327 eCRF.

Concomitant Medication

All medications (including, but not limited to, prescription or over-the-counter medicines such as aspirin, antacids, vitamins, mineral supplements, and herbal preparations) used from the Baseline visit through the end of the study must be recorded on the appropriate eCRF. Any ongoing systemic or local therapy at the time of Termination visit in the previous study M10-877 or M10-880 will be automatically transferred onto the M11-327 eCRF.

Contact the AbbVie Medical Monitor identified in Section 6.1.5, if there are any questions regarding concomitant or prior therapy(ies).

Each vaccine administered to the subject should be listed as a concomitant medication on the Other Medications eCRF. Live vaccines may not be given concurrently while on study drug or for 70 days after the last dose of adalimumab.

Concomitant use of nutritional supplements should be recorded as concomitant medications (generic and/or brand name, dose [if known], frequency) on the Other Medications eCRF.

Dispense Study Drug

Study drug will be administered to subjects by study site medical staff, by himself/herself or by a designee (friend, family member or health care professional) throughout the study.

Subjects, a designated family member or friend, will be trained to administer study medication during the first visit or several times, if appropriate. This training must be documented in the subject's source document.

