6.1.4 Adverse Event Collection Period

[figure not shown]
All adverse events reported from the time of study drug administration until 70 days, following discontinuation of study drug administration have elapsed will be collected, whether solicited or spontaneously reported by the subject. In addition, serious adverse events will be collected from the time the subject signs the study-specific informed consent if the subject does not have the Baseline visit on the same day. Any adverse events experienced prior to first study drug administration in M11-327 will be reported in the parent protocol. Adverse event information will be collected and recorded on the appropriate eCRFs. In the event of a death, the date and reason for death should be collected.

Subjects will be contacted approximately 70 days following study drug discontinuation for an assessment of any new or ongoing AEs except those subjects who continue on adalimumab therapy after the end of study participation. These subjects are not required to complete the 70-day follow-up and any new Adverse Events should be reported through the mechanism used for all post marketing adverse experiences.

There may be instances where a 70-day follow-up phone call or clinic visit occurs after the locking of the clinical database. In this situation, any adverse events reported to AbbVie from this 70-day follow-up phone call or clinic visit will be evaluated for inclusion in the clinical database. All SAEs or Adverse Events of Special Interest, as defined by AbbVie, reported during the 70-day follow-up phone call or clinic visit must be captured in the clinical database. The 70-day follow-up phone call will not be required for any subject that initiates commercial adalimumab after the end of study participation.

Adverse event information will be collected as shown in Figure 2.

Figure 2. Adverse Event Collection

* Except for subjects who continue on adalimumab therapy after the end of study participation.

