8.1.5 Analysis of Safety

Treatment-emergent AEs will be summarized using descriptive statistics.

Treatment-emergent AEs are defined as events with an onset date on or after the first study drug administration until 70 days following the last study drug administration. In case of increasing severity of an existing AE, the worsening will be considered as a new AE with a new onset date.

AEs will be tabulated by system organ class and preferred term whereby the most current implemented MedDRA dictionary will be used. Also, summaries by severity and relationship to study drug will be done. Certain AEs, like serious or severe, leading to premature withdrawal, will be listed and described in detail. AEs of special interest for treatment with biologics will be defined in the SAP and analyzed separately.

Other safety variables like laboratory data and vital signs will be described by descriptive statistics as mentioned before. In addition, shift tables and listings will be provided for abnormal values whereby the normal range of the analyzing laboratory will be used.

The IDMC will undertake a comprehensive review and assessment of the cumulative safety data until the completion of Study M10-877 and Study M10-880. Please refer to Section 5.5.5.1 for additional information regarding IDMC review.

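### On same-day rollovers, an adverse event carried over from the parent study with onset dated the first-dose day can be counted as treatment-emergent in M11-327

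*SAP*

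**What the plan says.** SAP 11.1 counts as treatment-emergent "any event with an onset date that is on or after the first dose of adalimumab in Study M11-327", up to 70 days after the last dose. Protocol 8.1.5 starts its definition in the same way: "Treatment-emergent AEs are defined as events with an onset date on or after the first" study drug administration. Both rules include the first-dose day.

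Three protocol statements determine what can fall on that day:

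- **Visit timing (5.1).** "Study M11-327 Baseline (Week 0) visit will be performed on the same day as the Final/Early Termination visit in the parent studies". Dosing begins then: "Starting at Baseline, all subjects will receive open-label adalimumab 40 mg dose eow SC". A delay is permitted; the longest time allowed between the parent final visit "and the Baseline visit of Study M11-327 is 28 days".
- **Transfer (5.3.1.1, Adverse Events).** "Any ongoing adverse events at the time of the Termination visit in the previous Study M10-877 or Study M10-880 will be automatically transferred"; the destination is the M11-327 eCRF.
- **Ownership (6.1.4).** "Any adverse events experienced prior to first study drug administration in M11-327 will be reported in the parent protocol".

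SAP 11.1 also treats an event with an incomplete onset date as treatment-emergent unless something else shows that it was not. It treats worsening of an existing AE as a new AE with a new onset date. It provides a separate listing of pre-treatment events, but for SAEs only.

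**The concern.** The protocol intends M11-327 to report what happens after its own first dose. The date rule does not fully achieve this. When the parent final visit and the first dose share a date, an event that began earlier that day and was copied across has an onset date equal to the first-dose date, so the rule includes it.

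Long-term safety is the primary objective. A misclassified event would be reported in the parent study under protocol 6.1.4 and again in M11-327. For a subject who received placebo in the parent study, an event that preceded any adalimumab would appear as an event on adalimumab. The SAP would also treat the day inconsistently. Under SAP 6.1, a pressure reading taken on the first-dose day is a baseline value, and so sets the baseline category in the SAP 11.6 shift table. An AE based on that same reading would be classed as post-dose.

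**Working it through.** The plan gives no figure on this point, so there is nothing to reproduce. The check applies the rule to the possible cases.

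**Inputs**
- V = date of the parent final visit; D = date of the first M11-327 dose; gap g = D − V, default 0, maximum 28 days (protocol 5.1).
- O = recorded onset date. Protocol 6.1 lists the date of onset among the items to record, and no clock time.
- Only events ongoing at V are transferred (protocol 5.3.1.1).

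**Formula.** The day count takes the form in SAP 6.2, with no Day 0, anchored on the first M11-327 dose because SAP 11.1 uses that anchor:
- day = O − D + 1 if O ≥ D;
- day = O − D if O < D.

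An event is treatment-emergent if day ≥ 1 and O is no later than the last dose + 70 days.

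| Case | Day | Classified as treatment-emergent? |
|---|---|---|
| Ongoing at V, O = V, g = 0, began before the injection | 0 + 1 = 1 | Yes, although pre-dose |
| Found at V, but onset recorded 3 days earlier, g = 0 | −3 | No |
| O = V, g = 1, 14 or 28 | −1, −14 or −28 | No |
| Resolved by V | no record transferred | No |
| Ongoing at V, onset date incomplete | not defined | Yes by default, unless the parent record is accepted as contrary evidence |
| Transferred, then worsened after D | new onset date after D | Yes, and correctly |

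Only the first and fifth cases give a doubtful result. In the first, the allowance for contrary evidence does not help, because SAP 11.1 offers it only for incomplete dates. In the fifth, the result depends on how the SAP is programmed. The general date imputation in SAP 6.3.4 sets a missing start day to the first of the month, which would usually place onset before the dose. The specific AE rule in SAP 11.1 defaults to inclusion. The SAP does not say which governs, or whether the parent record counts as evidence.

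**Can the first case arise?** The documents allow it. On the visit day blood is drawn before study drug, and abnormalities noted after the parent baseline are to be assessed as possible AEs (protocol 5.3.1.1). Eligibility, including intraocular pressure and lens opacity, is also judged at that visit (protocol 5.1 and 5.2.2).

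**Effect on the tables.** The rate per 100 subject-years in SAP 11.1 counts every event, so each misclassified record adds one to the numerator. The percentage of subjects counts a subject once, so it changes only if that subject has no other qualifying event during follow-up.

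**The case against.** The case for leaving the rule alone has four parts.

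1. **Onset is not detection.** The rule uses the recorded onset date. A finding first seen at the parent final visit may well be dated earlier, and is then excluded. This stands. A reader might infer that every event found at that visit becomes treatment-emergent; the documents do not support that.
2. **Several conditions must coincide.** The rollover must be same-day, the event must be ongoing, and its onset must be dated exactly that day or left incomplete. This also stands and limits the point.
3. **The intent is already clear, and the SAP follows the protocol.** Protocol 6.1.4 assigns pre-dose events to the parent study, and protocol 8.1.5 uses the same inclusive definition, so the SAP has not departed from the protocol's definition. Its wording could also be read as referring to the dose itself and not its date. All of this is fair. But the protocol's allocation of pre-dose events is not carried into the SAP rule, and with only an onset date specified the rule will in practice be programmed on dates.
4. **Counting Day 1 is a conservative convention.** It can over-count but cannot hide an event, and the analysis is single-arm and descriptive, so no test is affected. The convention is reasonable when the order of event and dose is unknown. It does not answer this case: an event already ongoing at the parent termination visit is, by the protocol's own allocation, a parent-study event.

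**Conclusion.** The concern holds in a narrow form. On a same-day rollover, a transferred ongoing AE with a recorded onset on the first-dose date, or with an incomplete onset date, can be counted as treatment-emergent in M11-327 when the protocol assigns it to the parent study. Events with a complete, earlier onset date are not affected, nor are complete dates in rollovers with a gap of at least one day.

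The size is unknown. The documents do not give the number of same-day rollovers, the number of transferred records dated that day, or the number with incomplete dates. No percentage or rate can be attached to the point.

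A reader might infer that the extra events cluster among the uveitis-related AEs, since treatment-failure subjects enter with active disease. That is plausible, but the documents do not show it: how parent sites dated examination findings, and whether they also entered treatment-failure findings as AEs, depends on parent-study procedures not described here. Nor do the documents support saying that the AE results are materially inflated. This is a gap in one stated rule that is worth closing, because safety is the primary objective and the correction is simple.

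**What to change.** Amend SAP 11.1 as follows.

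- A record transferred from the parent study is not treatment-emergent in M11-327 unless its severity increased after the first M11-327 dose. The existing text already makes such worsening a new AE.
- Identify transferred records by a transfer flag. Neither document says that one was kept; without it, match the parent and M11-327 records on subject number, AE term and onset date. Subject numbers carry over unchanged (protocol 5.3.1.1).
- List the excluded Day 1 events, including non-serious ones, alongside the pre-treatment SAE listing.
- Keep the inclusive Day 1 rule for events that were not transferred.
- Give a supporting AE table under the current rule.

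A new eCRF item asking whether onset came before or after the injection is not proposed. The SAP's own summary of changes notes that the second pivotal study had terminated, and with a maximum gap of 28 days the Baseline visits would be past, so the answers would be retrospective.

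The cost is a short SAP change, one filter or match, one added listing and one supporting table. The downside is that AE counts fall slightly, which the supporting table makes visible.
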